6.3 Preparation/Handling/Storage/Accountability

1. The investigator or designee must confirm appropriate temperature conditions have been maintained during transit and storage for all study intervention received and any discrepancies are reported and resolved before use of the study intervention.
2. Subjects should be instructed to store the drug at room temperature and not to leave the study drug in a vehicle. Study drug may be transported with temperature excursions beyond storage conditions. Further instructions on storage will be provided to the subject in the 'Instructions for Use' provided at the Baseline visit.
3. Only subjects enrolled in the study may receive study intervention and only authorized site staff may supply study medication. All study medication must be stored in a secure, environmentally controlled, and monitored (manual or automated) area in accordance with the labeled storage conditions with access limited to the investigator and authorized site staff.
4. The investigator, institution, or the head of the medical institution (where applicable) is responsible for study intervention accountability, reconciliation, and record maintenance (ie, receipt, reconciliation, and final disposition records).
5. Further guidance and information for the final disposition of unused study interventions are provided in the Study Reference Manual.

6.4 Measures to Minimize Bias: Randomization and Blinding

6.4.1 Randomization

Study Using Precoded Randomization Provided to Site

On Day 1 (Baseline Visit), subjects will be assigned a unique number (randomization number) in ascending numerical order at each study site. The randomization number encodes the subject's assignment to receive study interventions, either TER-101 2.75% ointment or ointment vehicle according to the randomization schedule generated prior to the study by the Statistics Department at sponsor's designee. Each subject will be dispensed blinded study interventions, labeled with his/her unique randomization number, throughout the study.

6.4.2 Blinding

Application of the TER-101 2.75% ointment and ointment vehicle will be randomized and blinded to both the subject and the investigator.

Blind break

In case of an emergency, where knowledge of the treatment assignment could influence the subject's care, the investigator has the sole responsibility for determining if unblinding of a subject's treatment assignment is warranted. Subject safety must always be the first consideration in making such a determination. If the investigator decides that unblinding is warranted, the investigator should make every effort to contact the sponsor prior to unblinding a subject's treatment assignment unless this could delay emergency treatment of the subject. The procedure for breaking the blind will be detailed in the clinical trial study manual. If a subject's treatment assignment is unblinded, the sponsor must be notified within 24 hours after breaking the blind.

If more than 2 of the first 6 subjects enrolled develop an AE including application site reactions requiring cessation of treatment, then the sponsor's Chief Medical Officer (CMO)/designee may be unblinded as to treatment assignment. The determination to unblind will be made by the CMO/designee and will take into account the number of subjects with such reactions and their severity. The CMO/designee will determine whether to: (a) continue enrollment; (b) modify the regimen to once daily; or (c) terminate the study.

In the event of a Quality Assurance audit, the auditor(s) will be allowed access to unblinded study intervention records at the site(s) to verify that randomization/dispensing has been performed accurately.

6.5 Study Intervention Compliance

When subjects self-administer study intervention(s) at home, compliance with study intervention will be assessed at each visit. Compliance will be assessed by subject e-diaries and during the site visits and documented in the source documents and electronic case report form (eCRF). Deviation(s) from the prescribed dosage regimen should be recorded in the eCRF.

If subject is demonstrating nonadherence with study drug application (see [Section 8.3.5](#)), adherence/compliance should be reinforced with the subject. If continued nonadherence is demonstrated at the next assessment, then the subject should be considered for discontinuation from the study as per [Section 7.1](#) after discussion with the medical monitor.

A record of the number and weight of the medication tubes dispensed to and applied by each subject must be maintained and reconciled with study intervention and compliance records. Intervention start and stop dates, including dates for intervention delays, will also be recorded in the eCRF.

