7 DISCONTINUATION OF STUDY INTERVENTION AND SUBJECT DISCONTINUATION/WITHDRAWAL

7.1 Discontinuation of Study Intervention

In rare instances, it may be necessary for a subject to permanently discontinue (definitive discontinuation) study drug treatment. If a subject discontinues study treatment due to reasons such as tolerability, other AEs, or other reasons, every attempt should be made for the subject to complete an early termination visit consisting of the Day 29 assessments. See the SoA ([Table 1](#)) for data to be collected at the time of discontinuation of study intervention and follow-up and for any further evaluations that need to be completed.

Reasons for removal from study intervention include any of the following:

- AEs.
- Pregnancy (see [Section 10.8](#) and [Section 8.4.5](#)).
- Disease-state criteria (eg, progressive disease that requires discontinuation of the study intervention)
- Protocol deviation
 - Noncompliance with study protocol

- Requires treatment not allowed in the protocol for disease flare/rescue.
- If the subject meets an exclusion criterion (either newly developed or not previously recognized) that poses a safety risk and precludes further study participation
- Sponsor decision.
- Subject request to discontinue study intervention or withdraws from the study (See [Section 7.2](#)). If subject request to withdraw is due to an AE or lack of efficacy, then AE or disease-state criteria, respectively, should be the reported reason for discontinuation.

See the SoA ([Table 1](#)) for data to be collected at the time of intervention discontinuation and follow-up and for any further evaluations that need to be completed.

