7.2 Discontinuation/Withdrawal from the Study

A subject may withdraw from the study at any time at his/her own request or may be withdrawn at any time at the discretion of the investigator for safety, behavioral, compliance, or administrative reasons. This is expected to be uncommon.

At the time of discontinuing from the study, if possible, an early termination visit should be conducted, as shown in the SoA ([Table 1](#)). If a subject discontinues or withdraws from the study due to reasons such as tolerability, other AEs, or other reasons, every attempt should be made for the subject to complete an early termination visit consisting of the Day 29 assessments. See SoA ([Table 1](#)) for data to be collected at the time of study discontinuation and follow-up and for any further evaluations that need to be completed.

The subject will be permanently discontinued both from the study intervention and from the study at that time.

If the subject withdraws consent for disclosure of future information, the sponsor may retain and continue to use any data collected before such a withdrawal of consent.

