8.3.5 Adherence to Study Agent

Adherence with twice daily application of the study agents will be monitored using an e-diary in which the subject will record date and time of application. The e-diary will be dispensed at the Baseline Visit and collected and reviewed at each visit. Adherence will also be monitored by weighing the medication tubes at the Baseline Visit prior to dispensing the study medication to the subject, and at in person visits on Day 15 and Day 29. If the subject has missed more than 2 or more doses in a 7-day period due to reasons related to noncompliance, then study staff will re-emphasize the importance of medication adherence. If the subject continues to consistently miss doses, other than for treatment hold due to local application site or tolerability concerns as described in [Section 6.2](#), then the sponsor should be notified, and the investigator and sponsor may consider discontinuing the subject for noncompliance, as per [Section 7.1](#). Subjects should also be queried by site staff at in person visits that the investigational product is being applied correctly.

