3.1 GENERAL STATISTICAL CONSIDERATIONS

Descriptive statistics (mean, standard deviation [Std Dev], median, minimum, and maximum) will be used for continuous variables; number and percentage of subjects will be used for discrete variables. In general, the last measurement prior to the first dose of study treatment will be used as the baseline value with exception of WI-NRS, where the score recorded on Day 1 describing the worst itch score 24 hours prior will be used as the baseline. Nominal visits will be used for by-visit summaries and analyses for safety evaluations (i.e., laboratory sampling, physical examinations, vital signs, and electrocardiogram). For efficacy evaluations of EASI, IGA, and TBSA, analysis visits will be used for by-visit summaries. Analysis visits are defined as below:

Analysis Visit*	Target Day	Range
Day 8	Day 8	Day 2 – Day 11
Day 15	Day 15	Day 12 – Day 21
Day 29	Day 29	≥Day 22

* If there are multiple observations in the range, then the record collected closest to the target day will be selected; if there are multiple observations that have equal distance from the target day, the latter one will be used.

All treatment group comparisons will be made at the 0.05 level using a two-sided hypothesis test, unless otherwise specified. Given the exploratory nature of this study, p-values from all significance tests will be reported without adjustment for multiplicity.

Summaries will be presented by each treatment group, ie, TER-101 2.75% ointment, Vehicle ointment.

All tabulations of summary statistics, graphical presentations, and statistical analyses will be performed using SAS[®] Version 9.4 or higher.

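### Withdrawing a subject from the study for continued nonadherence loses the Day 29 EASI if the exit visit falls on or before Day 21; a wording change would avoid it

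*Protocol*

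**What the plan says.** Three protocol sections allow withdrawal for nonadherence.

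- **6.5** calls for reinforcement first. After that, "If continued nonadherence is demonstrated at the next assessment, then the subject should be considered for discontinuation from the study", following discussion with the medical monitor and with reference to 7.1.
- **8.3.5** sets reinforcement at about two missed doses in 7 days. If the subject goes on missing doses, "the investigator and sponsor may consider discontinuing the subject for noncompliance". Holds under 6.2 are exempt: "other than for treatment hold due to local application site or tolerability concerns".
- **7.2** says a subject "may be withdrawn at any time at the discretion of the investigator for safety, behavioral, compliance, or administrative reasons", and adds "This is expected to be uncommon". The consequence is stated plainly: "The subject will be permanently discontinued both from the study intervention and from the study at that time".

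Section 7.1 lists noncompliance among the reasons for stopping study drug. For subjects who stop, "every attempt should be made for the subject to complete an early termination visit consisting of the Day 29 assessments". The Schedule of Activities has no visit after that one.

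SAP 3.1 assigns EASI to analysis visits by study day: Day 2 to 11 is Day 8, Day 12 to 21 is Day 15, and Day 22 onward is Day 29. Where several records fall in one window, "then the record collected closest to the target day will be selected". The primary endpoint is percent change in EASI at Day 29, analysed by MMRM with visits Day 15 and Day 29.

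**The concern.** Missing applications of ointment does not stop an assessor from scoring EASI two weeks later at a visit already in the schedule. Withdrawal for this reason therefore gives up a primary value that could have been collected, against the aim in Protocol 9.7 that subjects complete the required assessments.

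The loss may also be selective. Section 6.2 holds apply to severe local effects or a high tolerability score. A subject who skips doses because of milder stinging, or because the ointment does not seem to help, is not clearly exempt. Section 7.1 relabels an exit as an adverse event or disease-state exit only when the subject asks to leave for such a reason; a withdrawal started by the investigator has no such rule. The examples of informative missingness in 9.7 are lack of efficacy and adverse events, so an exit recorded as noncompliance could be classed as uninformative. The MMRM assumes missingness at random.

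Exits for adverse events, rescue need or lack of efficacy are outside this point.

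**Working it through.** **Inputs.** Visit windows: Schedule of Activities (Day 8, Day 15 and Day 29, each ±3 days). Analysis windows: SAP 3.1. Sample size: Protocol 9.2 (about 60 randomised, 15% dropout, about 50 completing). Allocation 1:1: Protocol 4.1. The Day 15 to Day 29 correlation r is not in the documents; 0.3 to 0.7 is assumed.

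**The plan's own figure.** 60 × 0.85 = 51, and 50 / 0.85 = 58.8, rounded up to 59. Both agree with about 60 randomised for about 50 completers. No effect size, SD or power is stated, so there is nothing else to reproduce.

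**Step 1: where an exit EASI falls.**

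| Event | Possible days | SAP analysis visit |
|---|---|---|
| Day 8 call (no EASI) | 5–11 | none |
| Day 15 visit | 15 − 3 = 12 to 15 + 3 = 18 | Day 15 |
| Exit visit on Day 19–21 | 19–21 | Day 15 |
| Exit visit on Day 22 or later | ≥ 22 | Day 29 |

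The Day 15 visit lies wholly inside the Day 12–21 window. The path that loses the value is: nonadherent at the Day 8 call, nonadherent again at Day 15, exit visit by Day 21. If the exit assessment is the Day 15 visit itself, it supplies a Day 15 value only. If a Day 15 EASI is followed by an exit EASI up to Day 21, both compete for one window, and the exit EASI may not enter the MMRM at all.

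Two other paths lose nothing. Nonadherence first seen at Day 15 is next checked at Day 29, and an exit visit on Day 22 or later counts as Day 29.

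**Step 2: delay needed to keep the value.** For a Day 15 visit held on Day 12, 15 or 18, the exit visit must follow by at least 22 − 12 = 10, 22 − 15 = 7 or 22 − 18 = 4 days.

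**Step 3: share of an arm.** One lost value is 1/30 = 3.3% of a randomised arm, or 1/25 = 4.0% of an arm of completers.

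**Step 4: precision.** With a fraction f = 1/n of Day 29 values missing and Day 15 observed, the SE is multiplied by sqrt((1 − r²)/(1 − f) + r²). For n = 50 and r = 0.3: sqrt(0.91/0.98 + 0.09) = 1.0092.

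| n in total | r = 0.3 | r = 0.5 | r = 0.7 |
|---|---|---|---|
| 50 | 1.0092 | 1.0076 | 1.0052 |
| 60 | 1.0077 | 1.0063 | 1.0043 |

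The SE rises by 0.4% to 0.9% per lost value.

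**Step 5: possible shift, for illustration only.** If m of 30 subjects in one arm are lost and their unseen Day 29 percent change differs from the rest by D points, the arm mean shifts by (m/30) × D. With assumed m of 1 to 3 and D of 10 to 40, the shift runs from (1/30) × 10 = 0.3 to (3/30) × 40 = 4.0 points. The documents support no particular m or D and no direction. The MMRM's use of Day 15 data, ignored here, could reduce the shift.

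**The case against.** The strongest case against is that the path is narrow and already partly covered. It needs two consecutive findings of nonadherence, a discussion with the medical monitor, a discretionary decision and an exit visit before Day 22. The missed-dose trigger in 8.3.5 is limited to misses from noncompliance. Dropout of 15% is planned for, and missing data are to be tabulated with reasons and classified before unblinding. The Day 15 value enters the MMRM, LOCF may pick up an exit EASI that the MMRM does not use, and the return-to-baseline analysis gives a second contrast. All of this stands, and it is why the point is a small one. None of it recovers the observation.

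A second argument is that an exploratory study of drug activity may reasonably end participation of subjects who do not use the drug, and that a Day 29 value after persistent non-use matters only under a treatment-policy question. This does not carry. The ES already analyses subjects as randomised whatever their adherence, and the PPES is the planned place to set noncompliant subjects aside. What does stand is that keeping low-adherence subjects may slightly dilute the ES estimate.

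A third argument is that keeping a subject to Day 29 means about two more weeks without other AD therapies. That is a real burden, but the subject may leave at any time, and 6.6.1 withdraws anyone who needs rescue. In those cases the Day 29 value would still be lost.

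**Conclusion.** The concern holds, at low priority. As written, withdrawal for continued nonadherence with an exit visit on or before Day 21 leaves no Day 29 EASI, and the loss is avoidable because the visit is already scheduled. This rests on the SAP windows being applied as stated and on the discretion actually being used. Its frequency cannot be derived from the documents, so no count is given.

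The precision cost is under 1% of the SE per value for r between 0.3 and 0.7. The stronger reason to act is possible selection: a few missing values that may be related to treatment, with unknown direction. Extra enrolment under Protocol 4.1 could restore numbers but would not remove selection by adherence.

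**What to change.** In Protocol 6.5, 8.3.5, 7.1 and 7.2, state that missed study drug alone is not a reason to withdraw a subject from the study, or to substitute an early termination visit for the scheduled Day 29 visit. Keep the Day 15 and Day 29 assessments and analyse the subject in the ES. Say also whether study drug continues or stops; the Day 29 visit can be kept either way. Leave the 6.2 holds, rescue withdrawal under 6.6.1 and the subject's own right to withdraw unchanged.

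Handle nonadherence through reinforcement, recording and the PPES. Neither document gives the PPES compliance criterion as a number, so set one and document it before database lock, when 9.4 already requires the exclusions to be settled.

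The cost is wording in four sections, with no added visit or procedure. The downside is the possible slight dilution of the ES estimate; the PPES shows the contrast only as far as its compliance criterion is fixed before unblinding.

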6.6 Prior and Concomitant Therapy

Any medication or vaccine (including OTC or prescription medicines, vitamins, and/or herbal supplements) that the subject is receiving at the time of enrollment or receives during the study must be recorded along with:

- Reason for use.
- Dates of administration including start and end dates.
- Dosage information including dose and frequency.

In addition, therapies utilized for AD in the 6 months prior to screening should also be captured in the eCRF. The medical monitor should be contacted if there are any questions regarding concomitant or prior therapy. Please see [Section 10.9](#) for excluded therapies for AD.

Acetaminophen, at doses of ≤ 2 g/day, is permitted for use any time during the study. Other concomitant medication may be considered case-by-case by the investigator in consultation with the medical monitor.

6.6.1 Rescue Medication

Use of rescue medication is not permitted in this study. Any subject requiring rescue therapy per investigator opinion should undergo the early termination visit consisting of the Day 29 assessments and be withdrawn from the study prior to receiving rescue therapy.

6.7 Intervention After the End of the Study

The Sponsor will not provide any additional treatments to subjects after they complete or discontinue the study.

7 DISCONTINUATION OF STUDY INTERVENTION AND SUBJECT DISCONTINUATION/WITHDRAWAL

7.1 Discontinuation of Study Intervention

In rare instances, it may be necessary for a subject to permanently discontinue (definitive discontinuation) study drug treatment. If a subject discontinues study treatment due to reasons such as tolerability, other AEs, or other reasons, every attempt should be made for the subject to complete an early termination visit consisting of the Day 29 assessments. See the SoA ([Table 1](#)) for data to be collected at the time of discontinuation of study intervention and follow-up and for any further evaluations that need to be completed.

Reasons for removal from study intervention include any of the following:

- AEs.
- Pregnancy (see [Section 10.8](#) and [Section 8.4.5](#)).
- Disease-state criteria (eg, progressive disease that requires discontinuation of the study intervention)
- Protocol deviation
 - Noncompliance with study protocol

- Requires treatment not allowed in the protocol for disease flare/rescue.
- If the subject meets an exclusion criterion (either newly developed or not previously recognized) that poses a safety risk and precludes further study participation
- Sponsor decision.
- Subject request to discontinue study intervention or withdraws from the study (See [Section 7.2](#)). If subject request to withdraw is due to an AE or lack of efficacy, then AE or disease-state criteria, respectively, should be the reported reason for discontinuation.

See the SoA ([Table 1](#)) for data to be collected at the time of intervention discontinuation and follow-up and for any further evaluations that need to be completed.

7.2 Discontinuation/Withdrawal from the Study

A subject may withdraw from the study at any time at his/her own request or may be withdrawn at any time at the discretion of the investigator for safety, behavioral, compliance, or administrative reasons. This is expected to be uncommon.

At the time of discontinuing from the study, if possible, an early termination visit should be conducted, as shown in the SoA ([Table 1](#)). If a subject discontinues or withdraws from the study due to reasons such as tolerability, other AEs, or other reasons, every attempt should be made for the subject to complete an early termination visit consisting of the Day 29 assessments. See SoA ([Table 1](#)) for data to be collected at the time of study discontinuation and follow-up and for any further evaluations that need to be completed.

The subject will be permanently discontinued both from the study intervention and from the study at that time.

If the subject withdraws consent for disclosure of future information, the sponsor may retain and continue to use any data collected before such a withdrawal of consent.

7.3 Lost to Follow-up

A subject will be considered lost to follow-up if he or she repeatedly fails to return for scheduled visits and is unable to be contacted by the study site.

The following actions must be taken if a subject fails to return to the clinic for a required study visit:

- The site must attempt to contact the subject and reschedule the missed visit as soon as possible and counsel the subject on the importance of maintaining the assigned visit schedule and ascertain whether or not the subject wishes to and/or should continue in the study.
- Before a subject is deemed lost to follow-up, the investigator or designee must make every effort to regain contact with the subject (where possible, 3 phone or video calls and, if

necessary, a certified letter to the subject's last known mailing address or local equivalent methods). These contact attempts should be documented in the subject's medical record.

- Should the subject continue to be unreachable, he/she will be considered to have withdrawn from the study.

Discontinuation of specific sites or of the study as a whole are handled in [Section 10.1.9](#).

